6. STUDY OUTCOMES

6.1 Feasibility Outcomes

Study feasibility includes multiple parameters. To assess the feasibility of conducting a 2x2 factorial trial of group-based integrative pain management in primary care safety net clinics, we have chosen key parameters, operational metrics, and goals for each metric as shown in Table 1.

Table 1. Feasibility Parameters, Metrics and Goals

Feasibility Parameter	Operational Metric	Goal
Recruitment (primary feasibility outcome)	Percent of confirmed eligible patients who are randomized	40% of confirmed eligible patients
Retention	Percent of participants who completed 3-month follow up survey	80% of randomized participants complete 3-month survey
Adherence	Average number of intervention sessions attended	Mean of six intervention sessions

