9. STATISTICAL CONSIDERATIONS

9.1 Sample Size Rationale

The study will enroll 40 participants. As a small pilot study designed to pilot the refined intervention, we did not conduct a formal power calculation but instead used a confidence interval approach to determine sample size, based on current recommendations for small samples. Findings from the pilot study are intended to help plan for a future trial by estimating key parameters. However, small trials often overestimate treatment effects and the convention of basing power calculations on pilot trials has received considerable scrutiny (Kraemer, 2006). Our approach will be to determine whether the effect size from the pilot is clinically meaningful (i.e., within an 80% confidence interval of a pre-determined effect size) and justifies proceeding with future research. To determine this, Cocks and Torgenson (2013) recommend that a pilot sample size should be at least 9% of the sample size of the planned main study.

Based on data of minimally important differences for PROMIS pain measures, our main study would aim to detect a standardized effect size of 0.25. Using our pilot data to estimate within group correlation and a sample size calculator designed for individually randomized group trials, we estimated a sample size of 360. Using Cocks and Torgenson's method, the corresponding pilot sample size should be at least 32. Using an estimated attrition of 20%, we aim to enroll 40 participants. With 20 participants randomized to each of the study interventions, we will have sufficient power to determine if the effect size estimated from the pilot is within the range of clinical significance using a one-sided 80% confidence interval. If the estimated effect is zero or less, the upper 80% CI will not contain our target effect size of 0.25, and we would not proceed with a main study. If the estimated effect size from the pilot is larger than zero, and the study procedures are feasible and acceptable, then we would have sufficient preliminary data to proceed with the main study.

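### Section 9.1 states as certain that an estimate of zero or less excludes 0.25 at the one-sided 80% level, but the design does not assure this, and the stop/proceed rule uses a different criterion from the interval

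*Combined protocol and SAP*

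**What the plan says.** Section 9.1 (Sample Size Rationale) replaces a power calculation with a confidence interval argument. The pilot is to show whether its effect is clinically meaningful, defined as "within an 80% confidence interval of a pre-determined effect size". The main study would target a standardized effect of 0.25. From "a sample size calculator designed for individually randomized group trials, we estimated a sample size of 360", and the rule that "a pilot sample size should be at least 9% of the sample size of the planned main study", the plan concludes that "the corresponding pilot sample size should be at least 32". It then continues: "Using an estimated attrition of 20%, we aim to enroll 40 participants". The interval is specified as one-sided at 80%, with 20 participants randomized to each intervention.

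The decision follows in two sentences. The stop sentence reads "If the estimated effect is zero or less, the upper 80% CI will not contain our target effect size of 0.25", and in that case there is no main study. The proceed sentence begins "If the estimated effect size from the pilot is larger than zero, and the study procedures are feasible and acceptable", and in that case the data suffice to go on.

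Section 6.1 sets the retention goal at "80% of randomized participants complete 3-month survey", which is 32 of 40. Section 9.2 plans baseline-adjusted mixed models with random intercepts for person within group, and compares each intervention at the factorial margin.

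**The concern.** An upper limit equals the estimate plus a multiple of its standard error. Whether an estimate of zero puts that limit below 0.25 is therefore a statement about the standard error, which depends on the number of completers, the gain from baseline adjustment and the loss from clustering. Section 9.1 asserts the result without any of these.

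The plan also moves from one criterion (is 0.25 inside the 80% interval?) to another (is the estimate above zero?) as if they were the same.

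At stake is the meaning of the go/no-go statement. A reader would take a stop as evidence that 0.25 has been excluded at one-sided 80%, and might take a positive estimate as compatible with 0.25. Neither is guaranteed.

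**Working it through.** **Inputs from the documents.** Target effect 0.25; main-study size 360; 9% rule; pilot size 32; attrition 20%; enrolment 40; one-sided 80% interval (all Section 9.1); retention goal 80% (Section 6.1). Each margin compares two equal halves: 20 vs 20 randomized, 16 vs 16 with 32 completers.

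**Assumptions.** The main study's alpha and power are not stated, so I show five conventional pairs. 360 is read as the total analysed unless noted.

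**1. The plan's own figures.** 0.09 × 360 = 32.4, which the plan gives as 32; 32 / 0.80 = 40. Both reproduce, but 32.4 has been rounded down: 32 / 360 = 8.9%, and the smallest whole number meeting the rule is 33. With 40 enrolled, 33 completers means 33 / 40 = 82.5% retention.

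**2. Where 9% can come from.** If the main study is sized so that 0.25 = (z_alpha + z_power) × SE, the pilot fraction at which the one-sided 80% limit at an estimate of zero equals 0.25 is (z_0.80 / (z_alpha + z_power))². Two-sided 5% with 80% power gives (0.8416 / 2.8016)² = 0.0902, and 0.0902 × 360 = 32.5. The other four pairs below give 0.115, 0.083, 0.079 and 0.067. The match to two-sided 5% and 80% power is an inference, not something the plan states.

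**3. Upper limit at an estimate of zero.** SE(n) = 0.25 / (z_alpha + z_power) × √(360 / n), and limit = 0.8416 × SE(n). Worked case (two-sided 5%, 80% power): 0.25 / 2.8016 = 0.08924. At n = 32: 0.8416 × 0.08924 × √11.25 = 0.252. At n = 40: 0.8416 × 0.08924 × 3 = 0.225.

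| Main-study error rates (assumed) | z sum | Limit, 32 completers | Limit, 40 completers |
|---|---|---|---|
| Two-sided 5%, 80% power | 2.8016 | 0.252 | 0.225 |
| One-sided 5%, 80% power | 2.4865 | 0.284 | 0.254 |
| One-sided 5%, 90% power | 2.9264 | 0.241 | 0.216 |
| Two-sided 5%, 85% power | 2.9964 | 0.236 | 0.211 |
| Two-sided 5%, 90% power | 3.2415 | 0.218 | 0.195 |

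If 360 already includes 20% attrition, 288 are analysed; with two-sided 5% and 80% power the limit at 32 completers is 0.8416 × 0.08924 × √(288 / 32) = 0.225.

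On the first row, 33 completers give 0.248 with a normal quantile and 0.2515 with a t quantile on 31 degrees of freedom.

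**4. Reference values only.** Unadjusted and unclustered with SD 1, the limit is 0.8416 × √(4 / 32) = 0.298 and 0.8416 × √(4 / 40) = 0.266. To bring these below 0.25, adjustment and clustering together must multiply the variance by less than (0.25 / 0.2976)² = 0.71 at 32, or (0.25 / 0.2661)² = 0.88 at 40.

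**5. The two criteria.** The sign rule stops at an estimate of zero or less. The interval excludes 0.25 when the estimate is below 0.25 minus the limit at zero. These cut-points coincide only if that limit is exactly 0.25. The gap between them is:

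- Two-sided 5%, 80% power: 0.25 − 0.2519 = −0.002 at 32 completers (estimates from −0.002 to 0 stop although 0.25 is not excluded); 0.25 − 0.2253 = +0.025 at 40 (estimates from 0 to 0.025 proceed although 0.25 is excluded).
- One-sided 5%, 80% power: −0.034 at 32 and −0.004 at 40.
- Two-sided 5%, 90% power: +0.032 at 32 and +0.055 at 40.

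If the true effect is 0.25, the chance that the estimate falls in the gap is |Φ(−0.25 / SE) − 0.20|. For the first pair this is 0.2% at 32 (SE 0.2993) and 2.5% at 40 (SE 0.2677). For the other two listed it is 2.9% and 0.4% (SE 0.3372, 0.3016), and 3.3% and 6.0% (SE 0.2587, 0.2314).

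**The case against.** The strongest reply is that nothing here shows the sentence to be false. The 9% is a borrowed rule, applied to an N from a separate calculator, so it does not reveal that calculator's error rates. Three of the five pairs satisfy the sentence at both 32 and 40 completers, as does 360 with attrition included. The one pair that matches 9% misses by 0.002 against a target given to two decimals; on that reading any main-study size up to 354 would meet it at 32 (0.8416 × 0.08924 × √(354 / 32) = 0.2498). The pilot is also expressly not confirmatory.

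Most of this stands, and it rules out two stronger readings. A reader might infer that the rule fails at the planned 32 completers; that rests on inferred error rates and a margin of 0.002. A reader might also infer from 0.298 and 0.266 that it fails even with full follow-up; but Section 9.2 plans baseline adjustment. At two-sided 5% and 80% power an unadjusted main study would need 504, so 360 already reflects a smaller variance or other error rates.

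What the reply does not remove is the unconditional wording, the rounding below the plan's own minimum, and the change of criterion. The last remains even where the stop sentence holds: at 40 completers under two-sided 5% and 80% power, small positive estimates proceed with 0.25 outside the interval. It is fair to add that the proceed sentence does not itself claim 0.25 is inside the interval. The inconsistency is with the plan's opening definition of its approach.

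**Conclusion.** The point holds as a wrongly stated property of a decision rule: the design does not assure that an estimate of zero or less excludes 0.25. The limit at zero runs from 0.218 to 0.284 at the planned 32 completers and from 0.195 to 0.254 at 40, assuming 360 analysed and the five pairs shown. That supports 'not assured', not 'fails', and it does not show that the pilot is too small for its feasibility aims. That 32 falls short of 9% of 360 follows from the plan's own numbers, and the mismatch between the interval and the sign rule follows from its own wording; neither needs an outside assumption.

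Severity is minor. The cut-points differ by at most 0.055 in the cases worked, with a chance of disagreement between 0.2% and 6.0% if the true effect is 0.25. The primary outcome, the share of confirmed eligible patients who are randomized, is unaffected.

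**What to change.** Keep 40 participants and revise Section 9.1 as follows.

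1. Replace the unconditional stop claim with a conditional one: give the expected upper one-sided 80% limit at an estimate of zero for 32 and for 40 completers, under the assumptions used to obtain 360, and say whether 360 includes attrition.
2. Correct the 9% figure from 32 to 33, and say that with 40 enrolled this needs 82.5% retention, slightly above the 80% goal. At 20% attrition, 33 would need 33 / 0.80 = 41.25, so 42 enrolled; stating the small shortfall is enough and avoids changing N.
3. Make the stop and proceed sentences consistent. Either keep the sign rule and drop the claim that a stop excludes 0.25, aligning the earlier interval sentence with it; or report the observed upper one-sided 80% limit from the Section 9.2 model and claim exclusion of 0.25 only when that limit is below 0.25.

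The cost is wording, using inputs that the sponsor must already have had to reach 360, and a slightly less favourable precision statement. No extra patients or data are needed.

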9.2 Statistical Analysis Plan

Descriptive analyses

Baseline characteristics of participants, including sociodemographics and health condition variables, will be summarized to determine sample generalizability, and compared to assess group equivalency. We will look at summary statistics for data cleaning (e.g., means, ranges)

and then consider distributions by randomized arm as a check of balanced distribution across groups.

Analysis of Feasibility. Feasibility outcomes will be analyzed by computing percentages, with 95% confidence intervals, of rates of retention and enrollment. We will also conduct a thematic analysis of qualitative responses on participants' experiences with the study and acceptability of group acupuncture.

Assessment of implementation, defined as quality and consistency of the intervention delivery across staff, will be focused on evaluating core components and content of IGMV and parameters in STRICTA guidelines for group acupuncture. IGMV facilitators will complete a short survey after each session documenting content and time spent on each component. Acupuncturists will complete charting for each treatment provided.

Analysis of Patient-Reported Outcome Measures. This study is powered to assess exploratory effects and pilot feasibility, not for confirmatory analysis. Nonetheless, we will analyze clinical outcomes in a manner similar to that planned for the main study to make a preliminary assessment of the strength of the effects; to identify any unexpected issues with missing data, skewed distributions, or outliers; and to refine the statistical analysis plan. Relative (mean \pm SD) measures of effect sizes will be calculated as change from baseline to post-intervention for all outcome variables. Planned analyses include: within group changes from baseline to Week 12, group acupuncture vs. no acupuncture, and IGMV vs. no IGMV.

Treatment effects will be estimated using a repeated measures ANCOVA approach. The framework is similar to a linear mixed models but it includes the baseline of the outcome as a covariate (and omits the baseline from the outcome vector), and the models will include indicators for assignment to acupuncture, IGMV, a categorical variable for time, and interactions between treatment indicators and time, as well as random intercepts for person nested within group to account for within-group and within-patient correlation of the repeated measures. Models with a three-way interaction between the two treatment indicators and time will be evaluated as a first step to assess for synergy between IGMV and group acupuncture. We will also calculate an interaction ratio to assess clinically meaningful antagonism or synergy between the two interventions, specified as interaction ratios of ≤ 0.80 or ≥ 1.25 .⁴⁶ If there is evidence of interaction, we will assess marginal effects of each intervention. If no evidence of synergy is identified, we will proceed with models that omit the three-way interaction term, to instead focus on main effects of each treatment type. This approach will optimally weight data for patients with different numbers of responses, and will provide valid estimates in the presence of missing data under relatively mild assumptions about how the missing data arise.⁴⁷ We will conduct intent-to-treat, per protocol, and complier average causal effects analyses; and exploratory as treated analysis (receipt of any group integrative health intervention and dose-response based on number of sessions attended). Outcomes will be normalized as needed to meet model assumptions; for outcomes which do not meet distributional assumptions of normality, other generalized linear mixed models or non-parametric approaches such as Kruskal-Wallis tests will be used. Secondary outcomes will also be analyzed using this approach.

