This is a pilot study using a 2x2 factorial randomized clinical trial design. The pilot tests two 12-week group-based models: group acupuncture and integrative group medical visits (IGMV). Our primary feasibility outcome is participant randomization, measured as the percentage of confirmed eligible patients who are randomized. Secondary feasibility outcomes include retention (percentage of participants who complete 3-month follow up survey), adherence to intervention, and intervention fidelity. Additional outcomes of interest are patient-reported outcomes that will be the primary focus of a larger trial. We will assess quality and variability of data at baseline and 3-month follow up for pain-related outcomes. Data will include patient-reported outcomes, electronic health record data, and qualitative interviews, focus groups and observations to assess multilevel individual, interpersonal and organizational outcomes.

Interventions and Duration

All participants will receive usual care and be randomized to group acupuncture, IGMV, both, or waitlist control. Participants randomized to group acupuncture will receive 12 weeks of once weekly acupuncture treatments delivered in a group setting, which consists of a common space with multiple reclining chairs. Participants randomized to integrative group medical visits will receive 12 weeks of once weekly group sessions that include psychoeducation on pain topics, movement, mind-body skills practice, and facilitated discussion designed for social support.

Sample Size and Population

Our target population is patients with chronic pain who receive care in primary care safety net clinics. For this pilot, we will recruit and enroll 40 English or Spanish-speaking adults with chronic pain for ≥ 3 months receiving care in San Francisco Department of Public Health primary care clinics are eligible for the trial.

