1.2 Secondary Objectives

Secondary objectives of the study are to test quality and variability of longitudinal data for patient-reported, pain-related outcomes. We will collect data at baseline and three-month follow-up. Factorial analysis will be performed to assess differences from baseline to three-month follow-up at the margins and inside the table.

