4.4 Data Collection and Randomization

- Following the consent process, CRCs will conduct a baseline assessment with study participants. Baseline data collection will include sociodemographic, pain symptoms, mood, daily activities and open-ended questions regarding social isolation, stigma, and experiences with pain care.
- After the baseline assessment, participants will be randomized to one of four groups (described in more detail below). To maintain participant flow and adequate staggering of acupuncture and IGMV, we will use computer-generated, randomly permuted blocks of 4 and 8, stratified by language. The database manager who will not be involved with enrollment will program the random allocation sequence; no other study staff will have access to generating the randomization sequence. The CRC will access the allocation

sequence using a programmed database that cannot be altered once the randomized condition is revealed.

- Participants randomized to study interventions will participate in weekly sessions for twelve weeks and those randomized to Integrative Group Medical Visits have the option to participate in focus groups immediately following the final weekly session.
- Three months after baseline, participants will complete validated surveys about pain symptoms, social isolation, quality of life, and other pain-related symptoms and open-ended questions about pain management.
- Three months after baseline, participants will also complete semi-structured interviews on participants' experiences living with chronic pain, and their perspectives on non-pharmacologic pain treatment, including participation in the study.
- Interviews will focus on participants' experiences treating chronic pain, perspectives on non-pharmacologic treatment, and experiences referring patients to the Integrative Pain Management Program (i.e., the larger RCT component of this study). These interviews will last 45-60 minutes and take place in-person or virtually at a private location of the participant's preference (e.g., the participant's office, UCSF Osher Center for Integrative Health offices, or via Zoom). At the time of the interview, participants will complete a brief demographic form (including gender, racial and ethnic identity, years of clinical experience, and chronic pain treatment experience). No EHR data of any kind will be collected for providers participating in the provider interview subsample.

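### With one survey after baseline, the repeated-measures terms in Section 9.2 are redundant and the person intercept is not identified; the language stratum is also left out

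*Combined protocol and SAP*

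**What the plan says.** The survey schedule is consistent wherever it appears:

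- Précis, Design and Outcomes: "We will assess quality and variability of data at baseline and 3-month follow up for pain-related outcomes".
- Section 1.2: "We will collect data at baseline and three-month follow-up".
- Section 4.4: "Three months after baseline, participants will complete validated surveys".
- Section 6.1, retention metric: "Percent of participants who completed 3-month follow up survey".
- Section 9.2 sets its contrast over the same interval: "within group changes from baseline to Week 12".

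Section 9.2 then says of the model that "it includes the baseline of the outcome as a covariate (and omits the baseline from the outcome vector". It lists acupuncture, IGMV, categorical time and treatment-by-time terms as fixed effects, with "random intercepts for person nested within group to account for within-group and within-patient correlation of the repeated measures". Synergy comes first: "Models with a three-way interaction between the two treatment indicators and time will be evaluated as a first step to assess for synergy". If there is no synergy, the three-way term is dropped. The section adds that the method weights patients suitably when they contribute unequal numbers of measurements.

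Section 4.4 stratifies randomisation by language. Language is not among the model terms in Section 9.2.

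Two places hint at longer follow-up. Section 3 gives about six months of involvement, with an interview three months after the intervention. Section 4.1 asks for availability of up to 24 weeks. Neither schedules a further outcome survey, and Section 4.4 places the interview three months after baseline.

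**The concern.** A repeated-measures model needs at least two outcome records for some participants. Once baseline becomes a covariate, the written schedule leaves one. The time terms, the person intercept and the sentence about unequal numbers of measurements then refer to data that the trial does not plan to collect.

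What is at stake is clarity rather than validity. The synergy step decides which model follows, so it should be written as it will be run. Section 9.2 also says that the pilot should help refine the analysis plan, and a model that cannot be fitted as written does not test that plan. Separately, leaving out the stratification factor passes over an almost free chance of precision.

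**Working it through.** **Inputs.** Surveys per person: 2 (Précis, Sections 1.2, 4.4 and 6.1). Model terms: Section 9.2. Main-study size 360, pilot fraction 9%, attrition 20%, enrolment 40: Section 9.1.

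**1. The plan's own figure.** 0.09 x 360 = 32.4, which the plan states as at least 32. Then 32 / 0.80 = 40, so the enrolment target reproduces. Equal allocation and 20% loss leave 40 x 0.80 = 32 completers, or 8 per cell.

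**2. Outcome records.** 2 surveys - 1 baseline used as covariate = 1 per person.

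**3. Fixed effects.** Let A be acupuncture and B be IGMV. With one outcome time, the time column is constant, so time = intercept, A x time = A, B x time = B, and A x B x time = A x B.

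| Fixed-effect columns | One follow-up | Two follow-ups |
|---|---|---|
| Intercept, baseline, A, B, time, A x time, B x time | 7 columns, rank 4 | 7 columns, rank 7 |
| The same plus A x B x time | 8 columns, rank 5 | 8 columns, rank 8 |

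The distinct columns are those of a single-time ANCOVA: intercept, baseline, A and B, plus A x B in the synergy model. The two projections agree to 4e-16. Residual degrees of freedom, before any group effect, are 32 - 4 = 28 and 32 - 5 = 27.

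**4. Variance components.** With one record per person:

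- Var(Y) = person variance + residual variance + group variance.
- Cov between two people in the same group = group variance; between groups it is 0.

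Person and residual variance enter only as a sum. The table gives the REML log-likelihood for simulated data with 32 completers, with the person and residual variances summing to 1 and no group variance.

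| Person share | One follow-up | Two follow-ups |
|---|---|---|
| 0 | -14.594 | -35.019 |
| 0.25 | -14.594 | -32.194 |
| 0.50 | -14.594 | -30.417 |
| 0.75 | -14.594 | -32.884 |
| 0.90 | -14.594 | -55.998 |

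The one-follow-up likelihood is exactly flat. Group variance does still move it (-14.594, -14.680 and -14.876 at group variances 0, 0.1 and 0.3), so the group intercept remains estimable in principle.

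**5. Fitting.** In 200 simulated datasets with 8 assumed groups of 4, R lme4 refused the model with person nested in group every time, because there are as many persons as observations. ANCOVA with the group intercept alone ran in all 200.

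**6. Language.** If language explains a share R2 of the variance left after baseline, the SE without it relative to the SE with it is about sqrt(1 / (1 - R2)). The documents give neither R2 nor the language split, so both are assumed (splits 20/20, 28/12 and 32/8; 12,000 simulated trials per setting; no group effect).

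| Assumed R2 | Formula | Simulated ratio |
|---|---|---|
| 0% | 1.000 | 0.995 |
| 5% | 1.026 | 1.023 |
| 10% | 1.054 | 1.052 to 1.053 |
| 20% | 1.118 | 1.120 to 1.123 |

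In a separate simulation (32 analysed, assumed 16/16 split, baseline correlation 0.5, language effects of 0.25 to 0.8 SD), nominal 95% intervals covered 94.8% to 97.0% without language and 94.4% to 95.4% with it. Omission makes intervals somewhat conservative; it does not bias the estimate.

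**The case against.** The strongest defence is that Section 9.2 deliberately follows the main-study analysis, and that any competent statistician would drop the redundant terms. The reduction is unique, and a model that stops with an error cannot publish a wrong number. This stands, and it is why the point is minor. It explains the wording but does not make the model fit one follow-up.

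A second defence is that the six months in Section 3 and the 24 weeks in Section 4.1 imply a later assessment. If a second outcome survey was intended, the time terms and person variance would carry information. No section schedules one, so the question is open and the fix covers both cases.

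A third is that language adjustment is optional in a 40-person exploratory analysis. That is fair: its benefit rests wholly on assumed prognostic strength.

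Three stronger readings are tempting but unsupported:

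- *Standard errors become too small.* A fit with a person intercept only, in statsmodels with its default optimiser, gave 89.7% coverage for nominal 95% intervals in the main-effects model. That is not the planned model, and the documents name no software. With person nested in group (8 assumed groups of 4, time terms removed), the SE was 1.00 or more times the ANCOVA SE (median about 1.05), and coverage was 94% to 98%.
- *A meaningless person variance will feed the main-trial design.* No section says that it will be used. Section 9.1 relies on within-group correlation, which remains estimable in principle.
- *The decision to proceed is compromised.* The rule in Section 9.1 turns on whether the estimated effect exceeds zero, together with feasibility and acceptability. The estimate is the ANCOVA one.

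**Conclusion.** The point holds and is minor. On the written schedule, 3 of the 7 fixed-effect columns are redundant, as are 3 of the 8 in the synergy model. The synergy test is a two-way interaction, the person intercept is not identified apart from the residual, and the sentence on unequal numbers of measurements does not apply. These results follow from the schedule and the listed terms alone, and would change only if a second post-baseline outcome survey exists.

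Treatment effects, the two-way interaction and the interaction ratio all remain estimable. The percentage randomised, which is the primary feasibility outcome, is untouched. The language omission is the smaller part: the SE is about 2%, 5% or 12% wider than with language if it explains an assumed 5%, 10% or 20% of the remaining variance, and there is no gain if it explains nothing.

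**What to change.** First reconcile Sections 3 and 4.1 with the Précis and Sections 1.2, 4.4 and 6.1, and state whether any outcome survey follows the 3-month one.

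If none does:

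- Specify ANCOVA of the 3-month score on baseline, acupuncture, IGMV, acupuncture x IGMV and language. The interaction is the synergy test and is dropped for the main-effects model, as already planned.
- Keep the session-group random intercept. Remove the time terms and the person intercept.
- Replace the sentence on unequal numbers of measurements with a statement that completers are analysed, and that validity requires missingness to depend only on covariates in the model.

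If a later survey exists, name its time points, keep the repeated-measures model, include the acupuncture x IGMV term and add language.

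The cost is SAP wording, with no new visits or data. Language uses one residual degree of freedom (27 to 26 in the interaction model, 28 to 27 in the main-effects model), and the SE is about 0.5% wider if language explains nothing. If sessions are run by language, which the documents do not state, the group effect may already absorb part of any gain.
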